Combustible tobacco product smoking history
E-cigarette use history
Health Status (self-reported)
Enrollment in substance use/smoking cessation program/research study.
Interest in using smoking cessation medications
Medication history (use of any psychoactive medication)
For Women: Pregnancy status, current/plan for pregnant or breastfeeding

5. Assessment of Current Health Provider Relationship for HIPAA Consideration:

Does the Investigator or any member of the research team have a direct existing clinical relationship with any potential subject?

Yes, all subjects
 Yes, some of the subjects (POTENTIAL RELATIONSHIP)
 No

If yes, describe the nature of this relationship. [name] is pediatrician who provides clinical care at the Adolescent Clinic at the Yale New Haven Hospital primary Care Center. There is a potential risk that an eligible participant may have received care from [name] in the Primary Care Center, however this study does not recruit directly from the Primary Care Center and participation in the study will not affect the nature of the treatment the participants receive in the PCC.

6. Request for waiver of HIPAA authorization: (When requesting a waiver of HIPAA

Authorization for either the entire study, or for recruitment purposes only. Note: if you are collecting PHI as part of a phone or email screen, you must request a HIPAA waiver for recruitment purposes.)

Choose one:

For entire study
 For recruitment purposes only
 For inclusion of non-English speaking subject if short form is being used **and a translated HIPAA research authorization form is not available on the University's HIPAA website**

- i. Describe why it would be impracticable to obtain the subject's authorization for use/disclosure of this data;
- ii. If requesting a waiver of **signed** authorization, describe why it would be impracticable to obtain the subject's signed authorization for use/disclosure of this data;

Consent waiver will be requested for initial patient screening via telephone and Yale Qualtrics survey (Via text or web), done only to determine subject eligibility. We request a waiver for HIPAA authorization to obtain their phone number for voice and text and/or email as this method is equivalent to having a person leave their phone number on a voice mail and is being used to attract young adults to contact the research team.

Participants will provide verbal consent for the screening process and this consent is also included in the Qualtrics screening eligibility survey.

7. After eligibility has been decided, written consent will be requested from all participating subjects upon enrollment. It would be impractical to obtain written consent and consent for HIPAA authorization for phone screening procedures as screening will be done on the phone, text, or web

By signing this protocol application, the investigator assures that the protected health information for which a Waiver of Authorization has been requested will not be reused or disclosed to any person or entity other than those listed in this application, except as required by law, for authorized oversight of this research study, or as specifically approved for use in another study by an IRB.

Researchers are reminded that unauthorized disclosures of PHI to individuals outside of the Yale HIPAA-Covered entity must be accounted for in the “accounting for disclosures log”, by subject name, purpose, date, recipients, and a description of information provided. Logs are to be forwarded to the Deputy HIPAA Privacy Officer.

7. **Required HIPAA Authorization:** If the research involves the creation, use or disclosure of protected health information (PHI), separate subject authorization is required under the HIPAA Privacy Rule. Indicate which of the following forms are being provided:

Compound Consent and Authorization form
 HIPAA Research Authorization Form

8. **Consent Personnel:** List the names of all members of the research team who will be obtaining consent/assent.

[name], [name], RA- [name] and [name] (Maiden Name [name]).

9. **Process of Consent/Accent:** Describe the setting and conditions under which consent/assent will be obtained, including parental permission or surrogate permission and the steps taken to ensure subjects' independent decision-making.

After the screening process is complete and subject is found to be eligible, the RA/PI will schedule them for an in person intake. At this intake, all eligible participants will be asked for written consent using the Yale HIC approved combined consent/HIPAA form. All eligible participants will also be asked to provide contact information in the following manner. In addition to providing their own personal contact information, participants will be asked to give the names of two friends or relatives whom we can contact to obtain this information. We will contact these individuals only if we are unable to contact the participant directly and then only for the purpose of obtaining forwarding address and phone number. We will inform the person that the participant has authorized us to contact them and they will be asked if they are willing to give out this information. If they decline, they will not be contacted again. The participant will be advised that these people that you have given us their name and information so if we need to call them they are already aware. Participants will be given the option to list a contact person from an office/clinic that they attend for medical are. If they choose to list this contact, we will ask the participant to

sign a release so we can call the office/clinic if we have difficulty finding the participant for follow-up interviews. If the participant is unable to complete an in-person or phone interview, we may send them a follow-up questionnaire with a self-addressed, stamped envelope. If they are unable to come to the clinic but are willing to complete an interview we will meet the participant at a public place to collect a breath carbon monoxide sample and salivary cotinine sample, and questionnaire data.

10. Evaluation of Subject(s) Capacity to Provide Informed Consent/Accent: Indicate how the personnel obtaining consent will assess the potential subject's ability and capacity to consent to the research being proposed.

Through the verbal interaction with the potential subject, the PI or research assistant will make an assessment of the subject's ability and capacity to consent to the research. Participants must be young adults, therefore we do not expect that they will be a higher than usual risk of having fluctuating, limited, or diminishing decision-making capacity during the course of the research study,

11. Documentation of Consent/Accent: Specify the documents that will be used during the consent/assent process. Copies of all documents should be appended to the protocol, in the same format that they will be given to subjects.

Yale HIC-approved compound consent and authorization form and a separate written permission to allow videotaping.

12. Non-English Speaking Subjects: Explain provisions in place to ensure comprehension for research involving non-English speaking subjects. If enrollment of these subjects is anticipated, translated copies of all consent materials must be submitted for approval prior to use.

N/A- Non-English speaking subjects do not meet inclusion criteria

13. Consent Waiver: In certain circumstances, the HIC may grant a waiver of signed consent, or a full waiver of consent, depending on the study. If you will request either a waiver of consent, or a waiver of signed consent for this study, complete the appropriate section below.

- Not Requesting a consent waiver**
- Requesting a waiver of signed consent**
- Requesting a full waiver of consent**

A. Waiver of signed consent: (Verbal consent from subjects will be obtained. **If PHI is collected, information in this section must match Section VII, Question 6**)

- Requesting a waiver of signed consent for Recruitment/Screening only**

If requesting a waiver of signed consent, please address the following:

- a. Would the signed consent form be the only record linking the subject and the research?
 Yes No
- b. Does a breach of confidentiality constitute the principal risk to subjects?
 Yes No

OR

c. Does the research activity pose greater than minimal risk?

Yes ***If you answered yes, stop. A waiver cannot be granted.*** Please note:

Recruitment/screening is generally a minimal risk research activity

No

AND

d. Does the research include any activities that would require signed consent in a non-research context? Yes No

SECTION VIII: PROTECTION OF RESEARCH SUBJECTS

Confidentiality & Security of Data:

a. How will the research data be collected, recorded and stored?

Research data will be collected from study subjects by the PI or trained Research Associates (RA) who has successfully completed all required HIC and HIPAA training, using the paper study forms approved by Yale HI. Subjects will also be able to complete these same forms via a laptop as a survey administered through the Yale Qualtrics program. These forms will only include the subject's unique identifier, which is assigned to the subject at the time of enrollment, to which only study researchers will have access.

See V.10.5. for description of data security plan for MetricWire app.

All information that is obtained in connection with this study will remain confidential and will be disclosed only with subject permission or as required by U.S. or State law. All collected data will be stored in locked files, in the locked study-dedicated office of the Principal Investigator, with access granted only to the study research team. Paper data will be computerized (entered into a study database) and password protected, with access granted only to the study research team. Data will only be reported in aggregate. Data will be deidentified prior to formal data analysis, making individual subject identification impossible.

b. How will the digital data be stored? CD DVD Flash Drive Portable Hard Drive Secured Server Laptop Computer Desktop Computer Other

c. What methods and procedures will be used to safeguard the confidentiality and security of the identifiable study data and the storage media indicated above during and after the subject's participation in the study?

All portable devices must contain encryption software, per University Policy 5100. *If there is a technical reason a device cannot be encrypted please submit an exception request to the Information Security, Policy and Compliance Office by clicking on url <http://its.yale.edu/egrc> or email [contact]*

Once enrolled, subjects will be given a unique study number, to which only members of our research team will have access. Study data will be kept protected and treated as confidential at all times. Computerized subject data will be password protected. Moveable devices will be encrypted to protect identifiable information, following University policy. Only study researchers will have access to the link between subject name and identifier.

d. What will be done with the data when the research is completed? Are there plans to destroy the identifiable data? If yes, describe how, by whom and when identifiers will be destroyed. If no, describe how the data and/or identifiers will be secured.

Any identifiable information that is obtained in connection with this study will remain confidential and will be disclosed only with subject permission or as required by U.S. or State law. Once enrolled, subjects will be given a unique study number, to which only members of our research team will have access. Study data will be kept protected and treated as confidential at all times. Computerized subject data will be password protected. Data will only be reported in aggregate. Data will be de-identified prior to formal data analysis, making individual subject identification impossible.

Upon completion of the study, all computerized subject datasets will be de-identified and stored in a password-protected study computer, to which only the PI, investigators and study personnel will have access. All paper files with subject information will remain in locked files in the study office of the PI, until they are destroyed, after all analyses are complete. At that time, all data will be destroyed using an approved method as performed by, or with the assistance of ITS Med.

e. Who will have access to the protected health information (such as the research sponsor, the investigator, the research staff, all research monitors, FDA, Yale Cancer Center Data and Safety Monitoring Committee (DSMC), SSC, etc.)? (please distinguish between PHI and de-identified data)

Only the PI, investigators and study personnel will have access to the data which will be kept securely on a password-protected server.

During an audit or program evaluation, representatives from the Yale Human Investigation Committee and from the National Institutes of Health may have access to subject data, but will strictly follow rules of confidentiality.

f. If appropriate, has a [Certificate of Confidentiality](#) been obtained?
We will not obtain a certificate of confidentiality

g. Are any of the study procedures likely to yield information subject to mandatory reporting requirements? (e.g., HIV testing – reporting of communicable diseases; parent interview - incidents of child abuse, elderly abuse, etc.). Please verify to whom such instances will need to be reported.

NO

SECTION IX: POTENTIAL BENEFITS

Potential Benefits: Identify any benefits that may be reasonably expected to result from the research, either to the subject(s) or to society at large. (Payment of subjects is not considered a benefit in this context of the risk benefit assessment.)

This study does not provide direct benefits to the participant. Although the proposed research poses minimal risks to participants, the benefits to scientific knowledge are numerous. The results from this study may help scientists understand how young men and women switch from cigarettes to e-cigarettes.

SECTION X: RESEARCH ALTERNATIVES AND ECONOMIC CONSIDERATIONS

1. **Alternatives:** What other alternatives are available to the study subjects outside of the research?

The alternative to participating in the proposed study is to not participate.

2. **Payments for Participation (Economic Considerations):** Describe any payments that will be made to subjects, the amount and schedule of payments, and the conditions for receiving this compensation.

Participants will receive payments per the schedule below (and Table 1)

STUDY 2

- \$15 for each in person study visit (\$30 total)
- \$50 for completion of the EMA procedures
- Up to \$14 for completion of 85% or more of the EMA prompts
- Up to \$56 for on-time and valid video recordings of breath CO measurement
- TOTAL Possible payment=\$150 (of which \$56 is earned through CM)

3. **Costs for Participation (Economic Considerations):** Clearly describe the subject's costs associated with participation in the research, and the interventions or procedures of the study that will be provided at no cost to subjects.

Subjects will be responsible for the costs associated with:

1. Purchasing their e-cigarette, e-liquid, or any other e-cigarette product components.
2. Transportation to and from study visits
3. Operating their cell phone

4. **In Case of Injury:** This section is required for any research involving more than minimal risk, and for minimal risk research that presents the potential for physical harm (e.g., research involving blood draws).

- a. Will medical treatment be available if research-related injury occurs?
- b. Where and from whom may treatment be obtained?
- c. Are there any limits to the treatment being provided?
- d. Who will pay for this treatment?
- e. How will the medical treatment be accessed by subjects?

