Hypothesis A: Young adult dual users, particularly males, will report lower satisfaction and higher withdrawal scores with episodes of e-cigarette use, in comparison to episodes of combustible tobacco product.

Aim 2: To examine gender differences in e-cigarette use patterns among young adult dual users.

Aim 3: To examine gender differences in e-cigarette use patterns among young adult dual users.

Hypothesis B: Young men will be more likely smoke/vape for the rewarding effects of nicotine.

Hypothesis C: Young women will be more likely to smoke/vape in response to contextual reasons.

Exploratory Aim: To examine sex differences in within-subjects' changes in cotinine levels during the dual use periods.

STUDY 2

2. Research Plan:

- a. **Overview:** In this one-year pilot study of 32 non-treatment seeking young adult e-cig/combustible tobacco product dual users (15 males/15 females), we will use smartphone-based ecological momentary assessment (EMA) to gather real-time data of e-cigarette and combustible tobacco product behaviors during a 1-week cig/e-cigarette dual use period. Participants will be eligible if they self-report use of e-cigarettes at least one day during the past 7 days and use of at least one other combustible tobacco product at least one day during the past 7 days. Participants will respond to daily random prompts assessing in-the-moment use of e-cigs/combustible tobacco products and the **subjective factors** (ratings of satisfaction and withdrawal) and **contextual factors** (location, activity, social cues) associated with each episode of use. They will also complete daily electronic diaries to document e-cigarette use episodes/day, amount of e-liquid used, combustible tobacco products smoked/day, nicotine concentrations and flavors used during the day, and how satisfied they were with the e-cigarette experience during the study. They will also be queried about whether they changed product constituents (flavors, numbers of flavors, nicotine concentrations). We will also collect markers of carbon monoxide and nicotine exposure (CO, cotinine) throughout the study.

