Daily Momentary Assessments: Participants will be randomly prompted with the MetricWire app up to 3x daily to provide data on e-cigarette/combustible tobacco product use in the last 15 minutes, the type of e-cigarette/combustible tobacco product used (brand/type), subjective factors (withdrawal) and the contextual factors surrounding the episode. **Subjective factors** will include *Mood* and *Withdrawal*. To maintain brevity during the random prompts, We will use the Mood and Physical Symptoms Scale (MPSS) to measure severity of five withdrawal symptoms (depressed, irritable, restless, hungry and poor concentration) and urge to smoke (craving).(65) Total score ranges from 5 to 25 with a higher score indicating a higher severity of withdrawal symptoms, we will use the International Positive and Negative Affect Schedule Short Form's measures of negative affect.(69) Participants will rate on a 5 point scale their agreement with experiencing the following emotion: (upset, hostile, ashamed, nervous, afraid). **Contextual factors** will include questions about *Companionship* (“During this smoking/vaping episode, who were you around?”) (smoker, person who is vaping, non-smoker, alone)), *Location* (“Where were you?”) (home, work/school, vehicle, bar/restaurant/store, other)), and *Activity* (“What were you doing?”) (eating/drinking a non-alcoholic beverage, drinking alcohol, working/reading/studying, traveling, socializing, other)). Participants will have 30 minutes to respond to random prompts; otherwise data will be considered lost. Each random prompt will be date- and time-stamped and record whether the assessment was completed, missed, delayed, or disbanded. *This method aims to accrue a representative sample of occasions focused on the participants' immediate state.*

STUDY 2

Daily Electronic (e-) Diaries: Participants will fill in daily night-time e- diaries via the app to provide data on e-cigarette use (episodes of e-cigarette use/ day) and combustible tobacco product smoking (# combustible tobacco products smoked/day). They will provide a rating of satisfaction with the e-cigarette they used during the day, and overall satisfaction rating of using their e-cigarette (1-10 Likert scales). Participants will record pictures of the e-cigarette(s) used during that day via the MetricWire app and provide a description of features. *We have chosen daily night-time e-diaries to minimize participant burden.*

STUDY 2

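### Hypothesis B is about using products for nicotine reward, but no instrument the protocol describes records reward or reason for use, and the analysis plan assigns it no variable

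*Combined protocol and SAP*

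**What the plan says.** Hypothesis B sits under Aim 3 of Study 2 and reads "Young men will be more likely smoke/vape for the rewarding effects of nicotine". Aim 3 has the same wording as Aim 2 and concerns e-cigarette use patterns by gender, so the aim does not say how reward is to be measured.

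The measures are described in several places of the Combined protocol and SAP:

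- **Random prompts** (Research Plan g, Daily Momentary Assessments): recent use, product type, and "subjective factors (withdrawal) and the contextual factors surrounding the episode". The withdrawal scale covers "five withdrawal symptoms (depressed, irritable, restless, hungry and poor concentration) and urge to smoke (craving". Affect is taken from the "International Positive and Negative Affect Schedule Short Form's measures of negative affect". Context means company, place and activity.
- **Nightly diary** (same section): amounts used and satisfaction: "They will provide a rating of satisfaction with the e-cigarette they used during the day". The overview adds liquid volume, nicotine strength, flavours and product changes.
- **Baseline** (Research Plan f): demographics, 28-day use history, dependence, self-efficacy and product features.
- **Biomarkers** (Research Plan a and h): CO and cotinine, which measure exposure.

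The Analysis Plan under Statistical Consideration covers Aims 1 and 2. It mentions satisfaction, withdrawal, e-cigarette use and contextual factors. It does not mention reward, motive or Hypothesis B.

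**The concern.** A hypothesis that men use *for* reward needs, at the least, a record of reward or of reason, for smoking as well as vaping. Withdrawal, urge and negative affect lie on the relief side, and the positive half of the affect scale is not listed. If nothing in the data set represents the construct, the analyst must either report that the hypothesis could not be examined or decide afterwards that satisfaction, urge, dependence or cotinine stands in for it. These proxies could point in different directions, and the choice would be made with the results in view.

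The stated product of this pilot is a set of effect sizes with 95% confidence intervals to guide later studies. For Hypothesis B there would be no such estimate of the construct named.

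**Working it through.** The question is whether a measure exists, so the main check sets the hypothesis against each described instrument.

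**1. Instruments against the construct**

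| Source | What it records | Nicotine reward? | Reason for use? |
|---|---|---|---|
| Prompt: withdrawal scale | five symptoms and urge | no | no |
| Prompt: affect items | five negative emotions | no | no |
| Prompt: context items | company, place, activity | no | setting only |
| Diary | amounts, product features, satisfaction | proxy at best | no |
| Baseline | use history, dependence, self-efficacy, product | no | no |
| CO, cotinine | exposure | no | no |

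Items described that directly measure reward or reason: prompts 0, diary 0, baseline 0.

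**2. The one plausible proxy, satisfaction**

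- The Study 2 summary and Research Plan a (Overview) list satisfaction among the ratings taken at the random prompts for each episode. The Overview names both product types. Aim 1 and Hypothesis A also presuppose satisfaction for both.
- Research Plan e (Primary Outcome) defines it as a daily rating of the e-cigarette. Research Plan g lists only mood and withdrawal as the subjective content of the prompts and places satisfaction in the diary, for the e-cigarette.

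On the first reading there is a per-episode rating for either product. On the second there are at most 7 ratings per person and none for combustible use. The text does not settle which applies. On both readings the item records how use felt, not why it happened, and neither is linked to Hypothesis B.

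**3. Does the sample-size statement cover it?** The stated 0.37 SD for 30 subjects reproduces as t(0.975, 29)/√30 = 2.045/5.477 = 0.373. It refers to a change in e-cigarette episodes per day from week 1 to week 2, so it has no bearing on reward.

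**4. What an added item would yield**

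- Ceiling: 3 prompts × 7 days = 21 per person. The item would appear only when use occurred in the preceding 15 minutes.
- The documents give no use-positive rate. Assuming 10% to 30%: 0.10 × 21 = 2.1 to 0.30 × 21 = 6.3, so about 2 to 6 episodes per person over both products. Eligibility needs only one day of each product in the past week, so low rates are plausible.
- Sex contrast, one summary value per person, common SD: half-width of the 95% CI = t(0.975, 2m − 2) × √(2/m).
  - m = 16 per sex: 2.042 × 0.354 = 0.72 SD.
  - m = 15 per sex: 2.048 × 0.365 = 0.75 SD.

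Both values of m are shown because the protocol gives 16 per sex in one place and 15 in others. The SD is that of the per-person summary and is not given in the documents.

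**The case against.** The strongest reply is that satisfaction is a reasonable stand-in for reward, and that the overview text has it rated at prompts for both product types. This has force. A reader might infer from the detailed procedures that nothing positive is ever recorded for a combustible episode. The documents do not establish that, because the summary and the Overview say otherwise. What can be said is that the passages conflict and that no variable is assigned to the hypothesis.

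A reader might also infer that Hypothesis C ("Young women will be more likely to smoke/vape in response to contextual reasons") fails in the same way. It does not. Company, place and activity are collected, and the Analysis Plan intends to evaluate contextual factors, so the sexes can be compared on the contexts of use. Linking use to context by association is a recognisable approach in this type of study.

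Third, the questionnaires are not reproduced, and the recruitment text refers only to a baseline battery. The finding therefore concerns the instruments the protocol describes. It does not show that no such item exists anywhere.

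Finally, this is an observational pilot with prompts kept short on purpose, and neither primary outcome is touched. That limits the severity. It does not remove the gap: a pilot can live with an imprecise estimate of its hypothesis, but here no estimate is planned.

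**Conclusion.** The point holds for Hypothesis B alone. Of the instruments described, none measures nicotine reward or reason for use, and the plan names no variable or analysis for the hypothesis. Following the plan leaves it unanswered or answered by a proxy picked later. The closest proxy is described inconsistently and would not capture motive on either description.

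This should be changed, but it does not threaten the primary outcomes. The conclusion assumes that the protocol's list of instruments is complete. If an unlisted item exists, naming it and tying it to Hypothesis B would resolve the matter. The precision figures (0.72 to 0.75 SD) assume one summary value per person and a common SD, and the 2 to 6 episodes per person rest on an assumed use-positive rate.

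**What to change.** 1. Add one single-choice item to every prompt that reports use of either product: *Main reason for this use: pleasure or effect of nicotine / relief of craving or withdrawal / people, place or activity / habit / other.*
2. State the analysis of Hypothesis B in advance: outcome, pleasure option chosen or not; logistic mixed model with sex as fixed effect and a random subject effect; report the male-female difference in the model-based proportion with its 95% CI. The Statistical Consideration section already provides for this model class. With few episodes per person the fit may be unstable, so name a simple per-person proportion as the backup summary.
3. Reconcile the summary and Overview with the Primary Outcome and Daily Momentary Assessments text on when satisfaction is rated and for which products.
4. If no item can be added, reword Hypothesis B to the sex difference in the satisfaction measure actually collected and drop the claim about reward as a motive. This overlaps with Hypothesis A, which already addresses satisfaction with emphasis on males, so the two would need to be distinguished.

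Cost: one extra tap on use-positive prompts, an app edit and a minor ethics amendment, with no new visits or staff. The downsides are slightly longer prompts, a coarse single item and a wide interval.
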